#### **6.6.3. Vital Signs**

A summary table of the maximum change from baseline (increase and decrease) through Day 1 and change from baseline on Day 7 will be provided for SBP and DBP, heart rate, respiratory rate, and body temperature for the Safety population. Listings for each, and weight, will be provided based on the Safety population for each visit.

#### **6.6.4. Electrocardiograms**

A data listing will be created for ECG.

#### **6.6.5. Physical Examination**

A data listing will be created for physical examination measurements.

#### **6.6.6. Other Safety Parameters**

A data listing will be created for abdominal examination for hepatomegaly.

Data listings will also be provided for chest X-ray and liver elastography performed at screening, and all liver MRI scans. All listings will be provided using the Safety population.

### **7. INTERIM ANALYSES**

#### **7.1. Introduction**

An interim analysis (IA) of safety and efficacy data will be conducted at one year after the last enrolled participant receives SB-525 (PF-07055480) infusion. As this is an open-label study, the sponsor may conduct unblinded reviews of the data during the course of the study for the purpose of safety assessment, facilitating dose escalation decisions, facilitating pharmacokinetic/pharmacodynamic modeling, and/or to support clinical development.

Additionally, an interim analysis of safety and efficacy data may be conducted to support interactions with the national or local health authorities related to the submission and/or registration of SB-525 (PF-07055480) for use in hemophilia A patients.

This study will use an external Data Monitoring Committee (eDMC). The eDMC is independent of the study team and includes only external members. The eDMC will convene approximately every 6 months until study completion to monitor the safety and efficacy of the participants. Ad-hoc meetings will be organized as needed [eg, to assess events of special interest or after receipt of a serious unexpected suspected adverse reaction (SUSAR)]. Specification details for the process and the outputs to be generated for eDMC review will be provided in the eDMC charter.

## **7.2. Interim Analyses and Summaries**

The IA summaries will be a subset of the analyses described in this SAP, with the calculations of the observation period for a participant being based on the date of discontinuation or the date of the interim analysis data cut (ie, observation period = date of data cut [or conclusion date] – date of IP infusion + 1). Possible outputs include ABR, AIR, FVIII activity, safety, and other exploratory endpoints.

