### 3.2.1. Annualized Infusion Rate

The FVIII Administration electronic case report form (eCRF) and e-Diary will be used to collect each participant's pre-IP infusion FVIII medication details (including reason for infusion) beginning 30 days prior to the Screening visit through the Baseline visit (eCRF), and from Baseline to just before the IP infusion (e-Diary).

For pre-IP infusion, the AIR will be calculated in two ways:

- $[(\text{number of FVIII replacement infusions for reasons other than prophylaxis prior to IP infusion}) / (\text{[date of IP infusion} - \text{date of screening}] + 30)] * 365.25$ .
- $[(\text{number of FVIII replacement infusions for any reason prior to IP infusion}) / (\text{[date of IP infusion} - \text{date of screening}] + 30)] * 365.25$ .

Reasons for FVIII replacement therapy other than prophylaxis will include selective prevention of bleeding, prophylaxis for invasive procedures, and bleeding. In case a frequency other than "Once" is selected, the number of FVIII infusions to be added to the numerator of the above will be calculated based on the frequency of FVIII infusions and duration of treatment. A frequency of once per day will be used for frequencies listed as burst, taper, and titrate.

For post-IP infusion, the annualized infusion rate will be assessed as  $[\text{number of FVIII replacement infusions starting at 3 weeks (ie, Day 22 post-IP infusion)} / \text{(number of days in the observation period for the participant in years)}]$ . If the participant discontinued from study before the end of the prespecified time period, the last date in the observation period will be the date of study discontinuation. For all participants, post-IP infusions (and days for the denominator) will be counted beginning on Day 22, and will stop counting when (the first of) any of the following things happen:

1. The subject completes or discontinues (this day will be counted if data were collected).
2. Data cut or freeze date (this day will be counted if data were collected).

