The number of days in the observation period will be calculated as (date of data cut [or conclusion date] – [date of IP infusion + 21 days] + 1), which will then be annualized within the AIR formula. All infusions during the observation time period for any purpose (to treat bleeding, for preventive purpose, perioperative, or if FVIII prophylaxis regimen is initiated or resumed) will be included in the calculation of AIR. If no FVIII replacement infusions are reported during an observation period, AIR will be reported as zero.

A within-participant absolute difference, as well as percent reduction from pre-IP infusion AIR, will be calculated and summarized for the pre-study infusion calculation method that includes FVIII replacement therapy for any reason.

The five yearly windows defined in [Section 5.2](#) will be used for this AIR analysis. An additional observation period is defined for the entire length of follow-up, >week 3 through Year 5.

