### 3.2.2. Annualized Bleeding Rate

The number of bleeding episodes (BEs) during 12 months prior to the Screening visit will be collected in the Hemophilia History eCRF directly and will be used as the pre-screening rate. This form does not distinguish between treated or untreated bleeding episodes, only “total” pre-screening rate will be available.

The post-IP treated ABR will be calculated as:

$$[(\text{number of BEs requiring FVIII treatment recorded for the participant starting 3 weeks after IP infusion}) / (\text{number of days in observation period for the participant})] * 365.25.$$

If a FVIII prophylaxis regimen is initiated or resumed for a participant, then the time period (beginning with the first day of prophylaxis initiation or resumption) will be excluded from the treated ABR. The bleeding events after prophylaxis initiation or resumption will be excluded and the time period while on prophylaxis regimen will be deducted from the observation period, as well.

For all participants, treated bleeds (and days for the denominator) will be counted beginning on Day 22, and will stop counting when (the first of) any of the following happen:

1. The subject initiates or resumes routine prophylaxis (first day of resumption will not be counted);
2. The subject completes or discontinues (this day will be counted if data were collected);
3. Data cut or freeze date (this day will be counted if data were collected).

The number of days in the observation period will be calculated as (date of day before start of prophylactic dosing [or date of data cut or conclusion date] – [date of IP infusion + 21 days] + 1) which will then be annualized within the treated ABR formula. If no treated

bleeding episodes are reported during an observation period, treated ABR will be reported as zero.

During the post-IP period, multiple concurrent BEs (eg, two or more BEs that occur on the same date and time but in different sites in a participant) will be recorded as one bleed for overall treated ABR, but as separate BEs for that participant for treated ABR by location type (one episode for each unique location type, if they are different). Both spontaneous and traumatic treated bleeds will be counted towards the derivation of overall treated bleeding rate. BEs associated with a surgical procedure (perioperative and/or during the surgical rehabilitation period) will not be included in the treated ABR calculation.

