## 5. GENERAL METHODOLOGY AND CONVENTIONS

All statistical analyses will be performed using SAS system version 9.4 or higher.

All summary statistics will be reported stratifying by cohort/dose level (planned or received, depending on the study population) and overall. Relative day 1 is defined as the date of visit “Day 0”, the start of the IP infusion.

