##### 5.2.1.1. Yearly Windowing

The following windowing option may be used when each yearly observation period used for analysis will be 365 days. Any dates beyond 1460 days will also be included with Year 5 for analysis. Post-infusion AIR and ABR yearly windowing begins with 3 weeks after the IP infusion where day is calculated relative to the IP infusion date. Post-infusion AE yearly windowing begins on the IP infusion date.

Window name	Derivation
Year 1	Day 22 $\leq$ Year 1 $\leq$ Day 365
Year 2	Day 365 < Year 2 $\leq$ Day 730
Year 3	Day 730 < Year 3 $\leq$ Day 1095
Year 4	Day 1095 < Year 4 $\leq$ Day 1460
Year 5	Day 1460 < Year 5

Further details of windowing will be described separately for each endpoint in [Section 2.1](#), as applicable.

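### SAP 7.2 counts the interim observation period from infusion, but SAP 3.2.1 and 3.2.2 count ABR and AIR from Day 22; applied as written, interim rates are understated by 21/D

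*SAP*

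**What the plan says.** SAP 3.2 leaves the first 3 weeks after infusion out of both AIR and ABR, because prior routine prophylaxis may still be running then. The endpoint definitions apply this to numerator and denominator together:

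- **AIR (SAP 3.2.1):** "post-IP infusions (and days for the denominator) will be counted beginning on Day 22". The period at a data cut is "date of data cut [or conclusion date] – [date of IP infusion + 21 days] + 1".
- **Treated ABR (SAP 3.2.2):** "treated bleeds (and days for the denominator) will be counted beginning on Day 22", with the same subtraction of the infusion date plus 21 days. If prophylaxis is initiated or resumed, "the time period while on prophylaxis regimen will be deducted from the observation period".
- **Yearly windows (SAP 5.2.1.1):** Year 1 for AIR and ABR runs from Day 22 to Day 365. AEs differ: "Post-infusion AE yearly windowing begins on the IP infusion date".

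SAP 7.2 describes the interim summaries as a subset of the SAP's analyses, then gives one period for a participant: "observation period = date of data cut [or conclusion date] – date of IP infusion + 1". It lists ABR and AIR as possible interim outputs and makes no exception for them. The planned interim "will be conducted at one year after the last enrolled participant receives SB-525 (PF-07055480) infusion". SAP 7.1 also allows further interim analyses to support dealings with health authorities on submission or registration.

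**The concern.** The 7.2 formula is almost the AIR formula of 3.2.1 with the 21 days left out. Because 7.2 says the interim outputs are a subset of the main analyses, the event count stays as 3.2.1 and 3.2.2 define it, from Day 22. A programmer who follows both sections would divide events from Day 22 onward by days from Day 1. The denominator then holds 21 days in which no event can count.

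The resulting error has one direction: ABR and AIR come out low, and the percent reduction from the pre-infusion rate comes out high. The same participant at the same cut would have one rate under 3.2 and another under 7.2, each traceable to the SAP. SAP 7.2 also does not repeat the prophylaxis stop for treated ABR, so the end of the period is left open as well.

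**Working it through.** The plan states no figure to reproduce; the check is date arithmetic.

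**Inputs**

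- Day numbering, SAP 5: "Relative day 1 is defined as the date of visit" Day 0, the start of the infusion. Day 22 is therefore infusion date + 21.
- Interim denominator, SAP 7.2: D = cut (or conclusion) date − infusion date + 1.
- Main denominator, SAP 3.2.1 and 3.2.2, no prophylaxis started: cut date − (infusion date + 21) + 1 = D − 21.
- Annualisation factor, SAP 3.2.2: 365.25.
- Planned interim, SAP 7.1: one year after the last infusion, so D = 365 + 1 = 366 for the last-dosed participant.
- Planned accrual, SAP 2.2: 20 months. If accrual took that long, the first-dosed participant has D ≈ 366 + 20 × 30.44 ≈ 975.

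**Formula.** For N events counted from Day 22:

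- rate under 3.2 = N / (D − 21) × 365.25
- rate under 7.2 = N / D × 365.25
- ratio = (D − 21) / D, so the relative understatement is 21/D, whatever N is (N > 0).

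**Results**

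| D (days) | Case | (D − 21)/D | Understatement |
|---|---|---|---|
| 183 | early discontinuation or early cut (illustrative) | 162/183 = 0.885 | 11.5% |
| 366 | last-dosed, planned interim | 345/366 = 0.943 | 5.7% |
| 731 | dosed one year earlier (illustrative) | 710/731 = 0.971 | 2.9% |
| 975 | first-dosed, 20-month accrual | 954/975 = 0.978 | 2.2% |

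**Worked example.** Assume 3 bleeds from Day 22, D = 366 and a pre-screening rate of 12 per year:

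- Under 3.2.2: 3/345 × 365.25 = 3.18 per year; reduction 1 − 3.176/12 = 73.5%.
- Under 7.2: 3/366 × 365.25 = 2.99 per year; reduction 1 − 2.994/12 = 75.1%.

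The reduction shifts by 1.5 percentage points. In general the shift is (post rate / pre rate) × 21/D. At D = 366 it is 0.1 × 5.74% = 0.6 points if the true post rate is a tenth of the pre rate, and 0.5 × 5.74% = 2.9 points if it is half.

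**Treated ABR with prophylaxis.** Suppose prophylaxis starts on Day 184 and the 3.2.2 stop is kept. The counted days are 183 − 21 = 162 from Day 22, or 183 from infusion. Three treated bleeds give 3/162 × 365.25 = 6.76 against 3/183 × 365.25 = 5.99 per year, again 11.5% lower. This combines the 7.2 start with the 3.2.2 stop, which is the lenient reading. If the stop were dropped from the denominator too, the gap would be wider, but I do not rest the point on that.

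**The case against.** The best defence is that 7.2 is meant only to set the end date. It calls the interim outputs a subset of the SAP's analyses, and those already fix the Day 22 start and already allow for a data cut. On that reading the specific endpoint rules prevail over a general parenthesis, and the from-infusion formula serves AEs and study duration. It can also be called inconsistent to let the 3.2.2 prophylaxis stop survive 7.2 while treating the 21-day offset as overridden.

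This is probably what the authors intended, but it is not what 7.2 says. The sentence that invokes the subset goes on to give its own explicit formula without restriction. By-year AE incidence uses the number of participants still followed at the start of each year (SAP 6.1.1), not observation days, whereas ABR and AIR do divide by an observation period. As for consistency, 7.2 is silent on prophylaxis but explicit on the start date, so the two are not on the same footing.

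Two parts of the objection stand. First, the direction depends on the numerator staying at Day 22. If someone also counted events from infusion, AIR would take in prophylaxis infusions from the first 3 weeks and the bias could reverse, although that would breach 3.2. Second, the effect is small: the analyses are descriptive, ABR and AIR are only possible interim outputs, and every participant still followed at the planned interim has a complete Year 1 rate that is unaffected.

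**Conclusion.** The inconsistency is real and should be corrected. Its effect is modest. With Day 22 event counts, as 3.2.1 and 3.2.2 require, the 7.2 denominator understates each non-zero whole-period interim ABR or AIR by exactly 21/D. For participants still followed at the planned interim that is at most 5.7%; larger errors need shorter follow-up. Zero rates, yearly windows built as in SAP 5.2.1.1 and the final analysis do not change. The accrual-based figure assumes the planned 20 months, and the percentage-point shifts depend on the assumed rates shown. Whether any interim rate has actually been computed with the 7.2 denominator cannot be told from the documents.

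**What to change.** Add a sentence to SAP 7.2 stating that interim ABR and AIR use the observation periods of 3.2.1 and 3.2.2, with the interim cut as the data-cut date. It should name the Day 22 start and, for treated ABR, the exclusion of time from prophylaxis initiation or resumption. Limit the from-infusion formula to outputs counted from infusion, such as AEs.

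If interim ABR or AIR has already been produced, check which denominator was used, and recompute only if it was the one in 7.2.

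The cost is one sentence, and the final-analysis code can be reused. Any recomputed interim rates would be slightly less favourable.

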## 8. APPENDICES

### Appendix 1. List of Abbreviations

Abbreviation	Term
AAV	Adeno-associated virus
AAV2/6	Adeno-associated vector 2/6
ABR	Annualized bleeding rate
AE	Adverse event
AESI	Adverse event of special interest
AIR	Annualized infusion rate
ATC	Anatomical Therapeutic Chemical
BE	Bleeding episode
BLoQ	Below the limit of quantification
BMI	Body mass index
bpm	Beats per minute
BU	Bethesda unit
cm	Centimeter
CRP	C-reactive protein
CTCAE	Common Terminology Criteria for Adverse Events
DBP	Diastolic blood pressure
DNA	Deoxyribonucleic acid
ECG	Electrocardiogram
eCRF	Electronic case report form
eDMC	External Data Monitoring Committee
ELISA	Enzyme-linked immunosorbent assay
EQ-5D-5L	EuroQoL five dimensions, 5 levels questionnaire
F	Fahrenheit
FVIII	Factor VIII clotting protein
Gal3BP	Galectin-3-binding protein
Grp78	Glucose-regulated protein 78
IA	Interim analysis
IC	Informed consent
ICF	Informed consent form
IL6	Interleukin-6
IP	Investigational product
IU	International units
kg	Kilogram
LFT	Liver function test
m	Meter
MedDRA	Medical Dictionary for Regulatory Activities
mL	Milliliter
mmHg	Millimeters of mercury
MRI	Magnetic resonance imaging
N/A	Not applicable

Abbreviation	Term
nAb	Neutralizing antibodies
PCR	Polymerase chain reaction
PT	Preferred term
rAAV	Recombinant adeno-associated viral vector
RNA	Ribonucleic acid
SAE	Serious adverse event
SAP	Statistical analysis plan
SBP	Systolic blood pressure
sEGFR	Soluble epidermal growth factor receptor
SoA	Schedule of Activities
SOC	System organ class
SUSAR	Serious unexpected suspected adverse reaction
TEAE	Treatment-emergent adverse event
VAS	Visual analog scale
vg	Vector genome
vWF	Von Willebrand Factor
WHO DD	World Health Organization Drug Dictionary
